Design and rationale of the Prevention of radial Artery occlusion after Transradial accEss using
NitroglyceriN (PATENS)

NCT03158532

Florianópolis, dec/04/2024

Design and rationale of the Prevention of radial Artery occlusion after Transradial accEss using NitroglyceriN (PATENS)

Abstract

Background

Radial artery occlusion (RAO) is an important access site complications after transradial catheterization (TRC). Acute loss of radial artery patency after TRC is thought be due to a thrombotic process, and a bigger sheath-to-radial-artery ratio could reduce the incidence of RAO. Nitroglycerin acts through the liberation of nitric oxide (NO), which promotes muscle relaxation and vasodilation. Leading to a bigger sheath-to-radial-artery ratio the nitroglycerin administration could help to keep the radial artery patency. The aim is to study if nitroglycerin is superior to placebo concerning incidence of radial artery occlusion, confirmed by vascular Doppler ultrasound, up to 24 hours after catheterization.

Methods/Design

PATENS is a national, multicenter, superiority, 2-by-2 factorial, randomized clinical trial. Two thousand one hundred twenty-eight patients submitted to TRC will be randomized to either nitroglycerin or placebo, administered intra-arterially through the sheath, in two different moments during TRC: after the arterial sheath insertion, at the beginning of procedure, and at the end of the radial procedure, before sheath removal.

Results

The primary efficacy objective is to test the hypothesis that nitroglycerin, dose of 500 mcg, is superior to placebo in decreasing rates of radial artery occlusion on ultrasound Doppler analysis up

to 24 hours after procedures. As secondary objectives, the trial will evaluate the incidence of radial artery occlusion 30 days after catheterization. Enrollment was initiated in August 2017, and the inclusion phase is expected to last until the second half of 2019.

Conclusions

The PATENS trial will help define the role of prophylactic nitroglycerin as a RAO avoidance strategy in patients with submitted to TRC.

Trial registration

ClinicalTrials.gov identifier: NCT03158532

Background

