The use of the transradial approach (TRA) for coronary catheterization has increased over the years, worldwide. Radial artery is nowadays utilized by default for percutaneous coronary procedures in many centers, thanks to the reduced rates of vascular and bleeding complications and easier post-procedural management. The use of TRA also improves patient comfort, saves costs and it has an equivalent procedural success when compared to the femoral approach.

Although it is widely accepted by cardiologists and patients, some problems still exist. One of the major limitations is the development of radial artery spasm (RAS), which can reduce success rates, leading to femoral conversion, and cause significant pain to patients. The incidence of RAS varies between 2% and 34%. Aiming prevent RAS, the use of prophylactic intraarterial vasodilators is

routinely recommended by experts, mainly verapamil or nitroglycerin. Most catheterization laboratories habitually use some medication to prevent RAS, however, it is not a consensus.

Another important complication, often underestimated, is the post-procedural radial occlusion (RAO). Incidence of radial pulse loss has been reported to range from 1% to 12%. The benign nature of such an event has been constantly emphasized due to the dual blood supply to hand from the palmar arch. Mostly, the occurrence of radial occlusion is asymptomatic, symptomatic radial occlusion requiring medical attention occurred in only 0.2% of patients, but hand ischemia caused by RAO has been described. The most important aspect is that once artery is occluded, it can not be used neither as access site for future catheterization, nor be used as a conduit for bypass surgery nor fistula formation in hemodialysis patients. The use of small caliber catheters, adequate dose of heparin administration, immediate sheath removal after procedure, patent hemostasis technique and short time of compressive bandage are the key elements to reduce the risk of artery occlusion. Notably the presence of radial pulse does not exclude radial occlusion due to presence of collateral circulation; it can be more accurately evaluated by absence of antegrade flow in vascular doppler ultrasound. In fact, many operators do not assess radial artery patency before discharge.

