Acute loss of radial artery patency after cardiac catheterization is thought to be due to a thrombotic process. Sheath insertion leads to local endothelial injury and cessation of blood flow in the radial artery, creating an environment conducive to thrombosis. RAO tends to occur early after transradial catheterization, and roughly 50% of patients have spontaneous recanalization of the artery within 1 month. Direct support for the thrombotic hypothesis has come from recent studies that have confirmed the presence of radial artery thrombus on vascular ultrasound, angiography, and pathology. Transradial catheterization can negatively affect radial artery structure as well. A study using optical coherence tomography found that 67% of radial arteries had intimal tears and 36% had medial dissections immediately after transradial PCI. A study of radial artery function after transradial catheterization found that flow-mediated dilatation was blunted up to 9 weeks. The

radial artery response to nitroglycerin was also decreased, suggesting that the impairment in function was more than just temporary damage to the endothelium and involved long-term changes to the smooth muscle layer.

Nitrates in intra-arterial have been widely studied in prevention of spasm. Nitroglycerin binds to the surface of endothelial cells and undergoes two chemical reductions to form nitric oxide (NO). The nitric oxide then moves out of the endothelial cell and into an adjacent smooth muscle cell, where it promotes the formation of cyclic guanosine monophosphate (cGMP), which promotes muscle relaxation. A bigger sheath-to-radial-artery ratio could reduce the incidence of RAO, indeed current data show that nitroglycerin intra-arterial at the end of the procedure reduce the incidence of radial artery occlusion, so the main objective of this study is to evaluate whether administration of nitroglycerin at the start of a transradial procedure may preserve the patency of the radial artery; as well, confirm if nitroglycerin administration just before sheath removal helps to keep the radial artery patency, probably mediated by vasodilation.

Methods

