This is a randomized, multicenter, double-blind, placebo-controlled phase III study (Clinicaltrials.gov identifier NCT 03158532) with an all-comers design, comparing the use of nitroglycerin to decrease the rate of radial artery occlusion after transradial catheterization. Using a 2-by-2 factorial design, we will randomly assign 2128 patients with a clinical indication for coronary angiography (ad hoc angioplasty allowed) or percutaneous coronary intervention (PCI) to receive either 500 micrograms of nitroglycerin or placebo (0,9% sodium chloride), administered intra-arterially through the sheath, in two different moments during transradial catheterization: shortly after the arterial sheath insertion and at the end of the radial procedure, before sheath removal. Written, informed consent will be obtained from each subject. The study protocol has been presented to the institutional medical ethical committee of all participating hospitals to comply with local standards.

Randomization and final acceptance into the study will take place after successful radial artery cannulation and guide wire advanced into the radial arterial lumen through the needle to allow exclusion of failed radial puncture.

Patient population

All eligible patients are aged 18 years or over with a clinical indication for coronary angiography (ad hoc angioplasty was allowed) or percutaneous coronary intervention (PCI) if the following pre-requisites are met: (i) choice of the operator to use the transradial access route and (ii) use of sheath size 5 or 6 French. Allen test was not obligatory performed. The exclusion criteria were: (I) primary angioplasty due to acute myocardial infarction; (ii) intubated patients; (iii) complications during procedure (cardiac arrest, pulmonary oedema, cardiogenic shock, and stroke); (iv) prior inclusion in this trial; (v) known allergy or intolerance to nitrates; (vi) patients medicated with continuous intravenous nitrates or whom received any nitrates on the last hour and (vii) use within 24 hours prior to randomization of phosphodiesterase inhibitors.

Outcomes

Primary outcome

RAO: incidence of radial artery occlusion as confirmed by the absence of antegrade flow in vascular high resolution duplex ultrasound, up to 24 hours after catheterization.

Secondary outcomes

Late RAO: incidence of radial artery occlusion as confirmed by the absence of antegrade flow in vascular high resolution duplex ultrasound, 30 days after catheterization.

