Comfort assessment: pain felt by the patient in the forearm, assessed using numeric pain rating scale. The 11-point numeric scale ranges from '0' representing one pain extreme (e.g. "no pain") to

'10' representing the other pain extreme (e.g. "worst pain imaginable"). Only the numbers themselves are valuable answers, meaning that there are only 11 possible answers in the 0–10 interval.

Spasm (operator evaluation): catheter friction, as experienced by the operator (subjective measure), on a predetermined score: 0. No resistance during catheter manipulation or pain reported by the patient; 1. No resistance during catheter manipulation, but with pain reported; 2. Light resistance during catheter manipulation; 3. Moderate to strong resistance during catheter manipulation; 4. Catheter trapping.

Procedure duration: total duration of the procedure, from sheath insertion to last catheter removal.

Radiation exposure: total radiation used in the procedure (mGy).

Study definitions

RAO: the absence of an antegrade flow in radial artery was recorded by doppler ultrasound study.

RAS: will be defined as spasm when: operator evaluation of spasm bigger than 2 by predefined scale; need of spasmolytic medication; access site conversion due to confirmed angiographic evidence of spasm.

Access site conversion: impossibility of complete procedure without another arterial site access. It may be due to spasm or anatomical reason, and should be confirmed with angiography.

Radial puncture attempt: defined as any skin puncture with positive blood draw through the needle.

Local hematoma: will be classified according to the EASY scale: I, ≤ 5 cm diameter; II, ≤ 10 cm diameter; III, > 10 cm but not above the elbow; IV, extending above the elbow; and V, anywhere with ischemic threat of the hand.

Major bleeding: will be graded according to the Bleeding Academic Research Consortium definition: Type 3 ((3a) bleeding with hemoglobin drop ≥ 3 and < 5 g/dL, or packed red cells transfusion; (3b)

bleeding with hemoglobin drop ≥ 5 g/dL, heart tamponade, bleeding requiring surgical intervention or bleeding requiring intravenous inotropic drugs; (3c) intracranial hemorrhage; subcategories confirmed by autopsy, imaging examinations or lumbar puncture; intraocular bleeding with vision impairment) or type 5 bleeding ((5a) possibly fatal bleeding, (5b) definitive fatal bleeding).

Transradial procedure

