Local anesthesia will be administered with a subcutaneous injection of 1% lidocaine after skin preparation. Radial artery access will be obtained using either anterior or counter-puncture technique based on the operator's preference, using a 21-gauge bare needle or 20/22 G sheath covered needle, following which a 5Fr or 6Fr hydrophilic sheath will be inserted over a guidewire. Then, the patient will receive the randomized solution (500 micrograms nitroglycerin or placebo), plus heparin 5,000 units through the radial sheath as an intra-arterial bolus. Additional heparin will be given in cases of PCI (total 100 UI/kg). Doses of heparin are used according to our study protocol. The use of additional medication, either vasodilators or analgesics, is left to operators' discretion.

No routine

intravenous sedation was given. Transradial coronary angiography and/or PCI will be performed according to standard techniques, by the choice of operators. At the end of procedure, and before sheath removal, four to five ml of blood will be aspirated through the sheath to remove any residual thrombus and in a blinded fashion, either a 500 micrograms nitroglycerin or placebo will be administered through the radial sheath. Then, the arterial sheath will be removed and hemostasis will be achieved.

Arterial hemostasis

A compression device designed to assist hemostasis of the radial artery after a transradial procedure will be applied according to a previously validated protocol. Immediately after procedure

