completion, the sheath is initially pulled by approximately 2 to 3 cm. The device is applied to the patient with the green marker (located in the center of the larger balloon) positioned exactly at the puncture hole to aid in the location, visualization and control of possible bleeding. The balloon is inflated with an adequate syringe injecting 15 ml of air with simultaneous and total sheath removal, resulting in the absence of active bleeding. If bleeding occurs, additional 3 ml of air is injected to obtain complete hemostasis. The device is then slowly deflated to the lowest allowable volume (minimum 7 ml) while maintaining hemostasis. If bleeding occurred, 1 ml of air was reintroduced from the bleeding point. Radial artery patency was evaluated utilizing plethysmographic and pulse oximetry evaluation, with sensor placed over the thumb or index finger, and occlusion (manual pressure) of the ulnar artery. Absence of plethysmographic waveform is indicative of interruption of radial artery flow. After 1 hour post diagnostic procedure or 2 hours post intervention, 3 ml of air is removed every 15 minutes. If bleeding occurs during any stage of device removal, the volume of air needed for hemostasis is again injected, restarting the deflation process 60 minutes later. When all the air is removed, and there is no bleeding, the device is removed and the access site is covered with a simple dressing. Dressing should not encircle the entire wrist.

Statistical analysis

The primary analysis of the study is a superiority comparison between the use of nitroglycerin to decrease RAO, in all randomized patients, based on the intention-to-treat principle.

Using our primary end point to estimate the sample size, we suppose to have a 30% reduction in RAO for each trial intervention, considering potential interaction between them. Estimating RAO prespecified in the primary outcome of approximately 11.7% without use of nitroglycerin, with an alpha level of 0.05 and a beta level of 0.20, the minimum estimated sample size per group was established as 1064 individuals. As we do not expect any subsequent loss of follow-up due to the short primary evaluation, the enrollment of 2128 patients would provide sufficient power to the

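### Does the missing scoring time for forearm pain spoil the factorial comparisons on that secondary outcome?

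*Combined protocol and SAP*

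**What the plan says.** The Secondary outcomes section lists "Comfort assessment: pain felt by the patient in the forearm, assessed using numeric pain rating scale". The text that follows gives the two extremes of the scale and limits the answers to the 11 whole numbers. It does not say when the patient is asked, what period the answer covers, or whether worst, average or current pain is meant. No other section supplies this. The definition reads as complete, so the gap does not come from redaction or a broken table.

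The Methods section places the two randomised doses "in two different moments during transradial catheterization: shortly after the arterial sheath insertion and at the end of the radial procedure, before sheath removal". The Transradial procedure section confirms the order: after the catheter work, blood is aspirated and "either a 500 micrograms nitroglycerin or placebo will be administered through the radial sheath"; the sheath then comes out and compression begins. In the Arterial hemostasis section a balloon device is inflated with 15 ml of air, plus 3 ml if there is bleeding. The next step is: "The device is then slowly deflated to the lowest allowable volume (minimum 7 ml) while maintaining hemostasis". Stepwise air removal, 3 ml each quarter of an hour, starts one hour after a diagnostic procedure and two hours after an intervention.

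Other outcomes are placed in time. Occlusion is assessed within 24 hours and again at 30 days. Duration has both ends fixed: "Procedure duration: total duration of the procedure, from sheath insertion to last catheter removal".

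On purpose, the Background mentions pain as a consequence of spasm, "which can reduce success rates, leading to femoral conversion, and cause significant pain to patients", and gives the aim of the end dose as to "confirm if nitroglycerin administration just before sheath removal helps to keep the radial artery patency". The Statistical analysis section sets a two-sided 0.05 level for secondary endpoints and does not say which of the two factors each one is compared on.

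**The concern.** Two treatments given in sequence are each tested by their own margin of the factorial table. An outcome recorded between them can respond to the first and not to the second. If pain was scored when the last catheter came out, the end-dose comparison would compare groups that had not yet been treated differently on that factor. Any difference would be chance, and a null result could be misread as evidence that the end dose does nothing for comfort. If pain was scored later, the score could also carry the end dose itself, sheath removal and a long spell of balloon compression, and the start-dose result would answer a broader question.

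Because the plan is silent, a reader cannot tell which case applies. At stake is the interpretation of one secondary outcome on one of the two factors, and the exact meaning of the other.

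**Working it through.** The plan gives no pain effect size, standard deviation or scoring time, so there is no figure to reproduce. The check is one of sequence.

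**Step 1: order of events.** From the Methods, Transradial procedure and Arterial hemostasis sections: sheath insertion, start dose, catheter work, last catheter removal, end dose, sheath removal, compression, stepwise deflation.

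**Step 2: place the score in that order.** Two things matter, the moment of asking and the period asked about.

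| Score taken | Period covered | Start-dose comparison | End-dose comparison |
|---|---|---|---|
| Before the end dose | Ends before it | Valid: catheterisation pain | Cannot reflect that dose |
| After the end dose | Catheter work only | Valid: recalled catheterisation pain | Mainly reflects pain before that dose, so says little about it |
| After the end dose | Extends past it | Valid: includes removal and compression | Valid: can reflect that dose |

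The start-dose column is valid in every row because allocation is randomised and blinded and the start dose precedes any possible score. In the third row the factorial layout balances the end dose across the start-dose groups, so the start-dose margin is still a fair average effect. In the end-dose column, the first row is uninformative but not biased: with no effect possible, a test at 0.05 keeps its nominal error rate. Scoring after the end dose is necessary for an informative comparison but not sufficient, as the second row shows.

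**Step 3: can compression time give the gap a size?** Removals needed = volume / 3 ml, rounded up. Time of last removal = 60 min (diagnostic) or 120 min (intervention) + 15 × (removals − 1), assuming the first removal falls on the hour and there is no re-bleeding.

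- 7 ml: 3 removals; 60 + 30 = 90 min, or 120 + 30 = 150 min.
- 15 ml: 5 removals; 60 + 60 = 120 min, or 120 + 60 = 180 min.
- 18 ml: 6 removals; 60 + 75 = 135 min, or 120 + 75 = 195 min.

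These figures describe how long the wrist is compressed. They do not say that pain was scored in that window or how much the score would move. Nor are they strict minimum times from the second dose. The clock runs from the procedure, and if the procedure is taken to end at last catheter removal, as in the duration outcome, the interval from the second dose is shorter. No bias or power loss follows from them.

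**Step 4: do the neighbouring outcomes share the gap?** Duration ends before the second dose by definition. Radiation belongs to the same period by inference. In the operator's spasm score, grades 2 to 4 are tied to resistance while the catheter is moved. Grades 0 and 1 differ only in whether pain was reported, which is also untimed. The score's contribution to the spasm definition uses values above 2, so that split does not affect it. No section says that end-dose effects on duration, friction or radiation will be claimed.

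**The case for a change.** The best case for a change is that in a factorial trial with staggered doses, the timing of an outcome decides which factor it can test. The plan applies a 0.05 threshold to all secondary endpoints without mapping them to factors. Compression starts to be released an hour later after an intervention than after a diagnostic procedure, so a score at a fixed clock time could find some patients compressed and others not. Analgesics are at the operator's choice and may affect a later score. Scoring at last catheter removal would match the duration outcome and the spasm pain that the Background describes.

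Part of this stands: the definition is incomplete, and readers need the scoring time and the recall period to interpret an end-dose result on pain. The rest does not lead to a change. Mixed compression status adds noise, but randomisation spreads it over the arms. Analgesic use after allocation is part of how care unfolds under each arm.

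The proposed scoring time is a preference. The outcome is labelled a comfort measure, and comfort may properly include sheath removal and compression; scoring before the second dose would rule out any study of the end dose on pain. That the pain is located in the forearm, while the device sits at the puncture site, leans towards catheter-related pain without settling it. A statement that end-dose results on duration, friction and radiation are uninformative would answer a claim the plan never makes.

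**Conclusion.** This is missing detail that analysts and authors fill sensibly when they report the outcome, and no change to the plan follows. The start-dose comparison on pain holds at any scoring time, with a meaning that depends on the period covered. The end-dose comparison on pain should be read as informative only if the score was taken after that dose and covers time beyond it. No size can be put on the gap, because the documents give no pain effect, variability or scoring time.

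The practical scope is also small. The Abstract says that "the inclusion phase is expected to last until the second half of 2019", and the document is dated December 2024. On the assumption that enrolment kept roughly to that expectation, pain has already been scored, and what remains is to describe what was done.

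The conclusion rests on the stated randomisation and blinding, and on the plan naming patency as the aim of the end dose. The primary occlusion analysis, the sample size of 2128 and the start-dose comparisons on duration, friction and radiation are unaffected.

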study. Continuous variables will be described as means and standard deviation and compared using Student's t -test for normally distributed variables or assessed using Mann-Whitney test when not normally distributed. Categorical variables are expressed as frequencies and group percentage and will be compared with the chi-square or Fisher's exact tests. To test the interaction between interventions, we used a multivariable logistic-regression model that included the two randomized treatments and their interaction as parameters. In the analysis of the primary and secondary end points, a two-tailed p value of less than 0.05 will be considered statistically significant. No prespecified interim analysis will be performed. All analyses will be performed using SPSS version 22 (SPSS Inc., Chicago, Illinois).

Discussion

Cardiac catheterization is a common procedure and is need in many clinical scenarios and many times repeated procedures are need. The use of TRA is increasing aiming to improve patient comfort, save costs and reduce rates complications. This implies that the occurrence of RAO should be considered because, once it's occurred, it is impossible to use radial access for future catheterization. In most cases RAO occurs promptly after the procedure and up to 50% of patients have spontaneous recanalization of the artery within 1 month. A palpable pulse does not exclude the diagnosis of RAO: collateral blood flow may supply the periphery of the radial artery distally to the occlusion, giving a false impression of radial artery patency. Therefore, RAO can often be undiagnosed. Radial artery patency is better evaluated with clinical testing as the reverse Barbeau's test and with Doppler ultrasonography. Many interventions are suggested to reduce the risk of RAO, mainly anticoagulation, patent hemostasis and a bigger sheath-to-radial-artery ratio. Although nitroglycerin promotes vasodilation and thus improves the sheath-to-radial-artery ratio, no recommendation is done to its routinely use. Handling confounding factors such as anticoagulation and hemostasis, this test has an ideal design to address the question of whether routine use of the

nitroglycerin approach is superior to not use with respect to the occlusion occurrence, including possible predictors.

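### Does the plan need to restrict spasm, procedure duration and radiation to the start-of-procedure dose?

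*Combined protocol and SAP*

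**What the plan says.** The opening paragraph of Methods describes a 2-by-2 factorial trial in which nitroglycerin or placebo is given "in two different moments during transradial catheterization: shortly after the arterial sheath insertion and at the end of the radial procedure, before sheath removal". The Transradial procedure section places the second injection after the angiography or PCI: "At the end of procedure, and before sheath removal, four to five ml of blood will be aspirated through the sheath", and the blinded solution follows.

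Under Secondary outcomes, spasm is scored as "catheter friction, as experienced by the operator (subjective measure), on a predetermined score", and the score levels refer to resistance felt while the catheter is being manipulated. Duration is defined as "Procedure duration: total duration of the procedure, from sheath insertion to last catheter removal". Radiation is the procedure total in mGy.

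The Statistical analysis section gives a sample size of 1064 per group, 2128 in all. It names the t-test and Mann-Whitney test for continuous variables and chi-square or Fisher's exact test for categorical ones. To test the interaction it adds a "multivariable logistic-regression model that included the two randomized treatments and their interaction as parameters". On significance it says: "In the analysis of the primary and secondary end points, a two-tailed p value of less than 0.05 will be considered statistically significant". No section states which factor is compared for each secondary outcome.

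**The concern.** Catheter friction, duration and radiation are settled by the time the second injection is given. For that factor they are pre-treatment variables, so any significant end-dose effect on them would be a false positive. A rule that declares every secondary end point significant at 0.05, with no contrast named, seems to leave room for such tests.

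A second worry is precision. If results were compared between the four randomized combinations, or as any nitroglycerin against none, the one meaningful contrast (start dose against placebo) would lose patients or be diluted. A real effect of the early dose on spasm or procedure time could then be missed.

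**Working it through.** **Step 1. Timing.** Set against the Transradial procedure section, the three definitions all close before the second injection in the usual case: friction during manipulation, duration at removal of the last catheter, radiation when imaging ends (inferred from the second dose being given when the procedure is over). Randomization takes place earlier, after the wire has been advanced, and dosing is double-blind. The end-dose allocation therefore has no route to these values. Two cases are not covered by the text:
- After access-site conversion, the radial part may end before the last catheter is removed.
- The composite spasm definition under Study definitions includes spasmolytic medication without a time window.

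**Step 2. Which groups does the plan mean?** The group size is used here only as a count: 2 × 1064 = 2128, so a group is half the trial, which is one margin of the factorial. A single cell would be 2128 / 4 = 532, a number the plan never uses. (From 11.7% and a 30% relative reduction, the usual two-sided pooled formula with 80% power gives 1140 per group, not 1064. That is a separate matter and does not bear on this point.) The tests named for continuous variables compare two samples, and no four-group test is listed. The Background ends with separate aims for the early and late doses, and the sample size assumes a reduction for each intervention.

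**Step 3. False positives if the end-dose tests were run.** Three tests, each at 0.05, each with a null that is true by design:
- Independent: 1 − 0.95³ = 0.143.
- Fully correlated: 0.05.
- Upper bound under any dependence: 3 × 0.05 = 0.15.
- With pain added, if it were scored before the second dose (its timing is not stated): 1 − 0.95⁴ = 0.185 under independence.
- With three interaction tests added to the first three: 1 − 0.95⁶ = 0.265 under independence, at most 6 × 0.05 = 0.30.

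Friction, duration and radiation arise from the same procedure, so independence is unlikely. The range for the three is 5% to 15%.

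**Step 4. Precision under other contrasts.** Cells of 532 in place of margins of 1064 raise the standard error of the start-dose effect by √(1064/532) = 1.41. For power, the documents give no effect size on these outcomes, so the SD values below are assumptions. In the any-versus-none contrast, 1064 of the 1596 treated patients had the start dose, so the effect shrinks to 1064/1596 = 2/3.

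| Assumed start-dose effect | Start dose, 1064 vs 1064 | Both vs neither, 532 vs 532 | Any vs none, 1596 vs 532 |
|---|---|---|---|
| 0.10 SD | 63.6% | 37.1% | 26.5% |
| 0.1216 SD | 80.1% | 50.9% | 36.7% |
| 0.15 SD | 93.3% | 68.7% | 51.5% |

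The losses in the last two columns are real, but they belong to analyses the plan does not describe. Neither matches 1064 per group.

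**Step 5. Is the start-dose margin sound?** A second dose given later cannot alter these outcomes or modify the first dose's effect on them. Pooling over it is therefore legitimate in the usual case, without the no-interaction assumption that a factorial margin normally needs.

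**The case for a change.** The best case for a change is that the contrast really is open. The logistic model names no outcome, is there to test interaction, and does not suit continuous duration or radiation. For those two the plan offers two-sample tests without naming the samples. The primary analysis is described only as a comparison of nitroglycerin use. Someone working after unblinding could, on the text alone, choose the start margin, the end margin, any versus none, or both versus neither, and Step 4 shows that the choice affects power. One sentence would close this at no cost in patients or alpha.

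Much of this stands. The timing argument is right, the contrast is not written down, and conversion and the composite spasm definition are loose ends. What does not follow is that the plan commits to a faulty analysis. Its threshold sentence sets a significance level and does not list the comparisons. Group size and choice of tests favour the margins. A test of a true null at 0.05 still has a 5% error rate, and a reader who sees an end-dose difference in something measured beforehand has an immediate explanation: chance. Such a comparison works as a negative control and would not support a claim of benefit.

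**Conclusion.** No change is called for. The plan omits a detail: it does not say that three procedural secondary outcomes are compared by the start-of-procedure factor. A sensible analyst would do that anyway, using 1064 against 1064 patients pooled over the second dose, and that comparison is valid under the plan as written. The exposure is conditional. If all three were also tested by end dose, the chance of at least one spurious finding would be 5% to 15%, and the timing would show it for what it is. The 1.41 standard-error factor and the power losses apply only to contrasts the plan does not describe.

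This rests on the usual sequence, in which catheter work and imaging finish before the second injection. Access-site conversion could break that sequence in some patients, and the documents give no rate for it. The primary outcome, sample size and alpha are unaffected.
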